4.2.2 Exclusion Criteria

- 1. Primary or secondary CNS lymphoma
- 2. T-cell rich B-cell lymphoma
- 3. Plasma cell leukaemia
- 4. POEMS syndrome (polyneuropathy, organomegaly, endocrinopathy, monoclonal protein, and skin changes)
- 5. Primary amyloidosis
- 6. Clinically significant (in the opinion of the investigator) cardiovascular disease, such as:
 - History of myocardial infarction, acute coronary syndromes (including unstable angina), coronary angioplasty/stenting/bypass grafting within the past 6 months prior to the date of consent
 - Class III or IV heart failure as defined by the New York Heart Association (NYHA) functional classification system
 - Severe cardiac arrhythmia requiring medication or severe conduction abnormalities
 - Poorly controlled hypertension (resting diastolic blood pressure >100 mmHg)
 - Clinically significant valvular disease, cardiomegaly, ventricular hypertrophy, or cardiomyopathy, QTc prolongation [defined as a QTc interval >450 msec (males) or >470 msec (females)] or other significant ECG abnormalities including 2nd degree (type II) or 3rd degree AV block or bradycardia (ventricular rate <50 beats/min)
- 7. Clinically significant (in the opinion of the investigator) cerebrovascular disorders or vascular dementia
- 8. Clinically significant (in the opinion of the investigator) intercurrent medical or psychiatric illness, including serious active infection
- 9. Significant neuropathy (Grade 3, Grade 4, or Grade 2 with pain)
- 10. Concurrent treatment with other experimental drugs
- 11. A daily requirement for prednisone at a dose of >10 mg/day (or steroid equivalent) at time of starting the first dose of study drug. Higher doses are permitted for primary disease symptomatic control during the screening period, after discussion with the medical monitor, but this must have been tapered to a dose of ≤10mg/day by the time treatment with DTP3 starts
- 12. Stem cell transplant (autologous/allogeneic) or CAR T-cell regimen within 12 weeks of the date of consent
- 13. Participation in another clinical trial with any investigational drug within 28 days prior to the date of consent
- 14. Prior (non-experimental) MM or DLBCL therapy within 28 days of the date of first dose of DTP3. Concomitant bisphosphonate therapy is permitted
- 15. Prior radiotherapy within 28 days of the date of consent. Localised palliative radiation therapy to a single site for symptomatic control is acceptable within this period
- 16. Anticipated need for concurrent radiotherapy during the study

- 17. Past or current history of other neoplasms, except for
 - Curatively treated non-melanoma skin cancer
 - Adequately treated in situ carcinoma of the cervix
 - Prostate adenocarcinoma with documented PSA value of <0.1 ng/mL within six weeks of the date of consent
 - Other cancer curatively treated, and with no evidence of disease for at least 3 years before the date of consent
- 18. Known HIV infection
- 19. Active hepatitis C virus (HCV) or hepatitis B virus (HBV). Patients who are positive for hepatitis B core antibody, hepatitis B surface antigen, or hepatitis C antibody must have a negative polymerase chain reaction (PCR) result
- 20. Ability to become pregnant (or already pregnant or lactating). However, those female patients who have a negative serum or urine pregnancy test before enrolment and agree to use two highly effective forms of contraception: i) oral, injected or implanted hormonal contraception [resulting in the inhibition of ovulation] and condom, ii) have an intra-uterine device and condom, iii) vasectomised partner [provided that the vasectomised partner is the **only** sexual partner of a woman of child bearing potential and that the vasectomised partner has received medical confirmation of surgical success or iv) **complete** sexual abstinence [sexual abstinence is considered a highly effective method **only** if defined as refraining from heterosexual intercourse: periodic abstinence (calendar, symptothermal, post-ovulation methods) is **not** acceptable] during the trial and for 6 months after the last dose of DTP3 are considered eligible. Where age appropriate, female patients must be given advice on potential germ cell donation and cryopreservation.
- 21. Male patients with partners of child-bearing potential [unless they agree to take measures not to father children by using one form of highly effective contraception (condom plus spermicide) during the trial and for 90 days after the last date of DTP3]. Where age appropriate, male patients must be given advice on potential germ cell donation and cryopreservation, Men with pregnant or lactating partners should be advised to use barrier method contraception (for example, condom plus spermicidal gel) to prevent exposure to the foetus or neonate.

4.3 Withdrawal criteria:

4.3.1 Withdrawal of treatment

Study treatment may be withdrawn by the investigator for any reason judged to be in the patient's best interests.

Typical criteria for stopping therapy would include (but not be limited to):

- Unacceptable (drug related) toxicity
- Clinical reasons not related to DTP3
- Evidence of disease progression
- Symptomatic deterioration
- Pregnancy
- Withdrawal of patient consent for further treatment

Withdrawal of treatment is **not** the same as withdrawal from the study and all patients stopping therapy should be encouraged to continue with protocol specified follow-up procedures.

4.3.2 Withdrawal from study

The investigator must make every reasonable effort to keep each patient on study for the whole duration of the trial. However, if the investigator removes a patient from the study or if the patient declines further participation, final off-study assessments should be performed before the start of any alternate non-protocol therapeutic intervention. All the results, evaluations and observations, together with a description of the reasons for withdrawal, must be recorded in the medical records and the electronic case report form (eCRF).

The following are recognised reasons for the investigator to withdraw a patient from the study:

- Withdrawal of patient consent for further study participation
- Serious violation of the study protocol (including persistent patient attendance failure AND/OR persistent non-compliance)
- Sponsor's decision to terminate the study
- Clinical reasons not related to DTP3
- Lost to follow up
- Death

4.4 Patient Replacement

During the dose escalation stage, non-DLT evaluable patients will be replaced.

During the dose expansion stage, non-response evaluable patients may be replaced, after discussion with the medical monitor, (up to a study maximum of 72 patients).

5. TREATMENT

This is a multi-centre Phase I/IIa dose escalation and subsequent cohort expansion study. Up to 37 DLT evaluable patients with MM or DLBCL will be entered into an initial dose escalation stage. A DLT evaluable, patient must have received at least 10 of the 12 scheduled Cycle 1 doses of DTP3 (unless a DLT prevented further DTP3 dosing). Subsequently at least 24 response evaluable patients with MM and at least 24 response evaluable patients with diffuse large B-cell lymphoma will be entered into an open label expansion stage. A response evaluable patient is defined as one who has completed at least one response assessment after at least two cycles of DTP3 or has documented disease progression at an earlier time point.

In both stages, DTP3 will be administered as a one-hour infusion three times per week (with an interdose interval of 40 h to 72 h, with a larger interval due to non medical reasons if approved by the medical monitor).

The patient's most recently available weight should be used when calculating the amount of DTP3 to administer (see Pharmacy Manual for details of how to calculate the amount of DTP3 to be used). The weight used to calculate the dose of DTP3 can have been taken up to 10 days prior to administration of the first dose of each cycle.

Treatment for any individual patient will comprise continuous four-week cycles until disease progression (as defined in Appendices A and B), unacceptable (drug related) toxicity, or study termination, whichever occurs first.

Should a patient achieve a CR (DLBCL) or \geq PR (MM) of at least 12 weeks duration, the TDSMC will review all available data for that patient (AEs, clinical efficacy, PK, PD, DTP3 dose intensity) and make a recommendation to the relevant investigator about whether to reduce the frequency of DTP3 administration.

5.1 Dose Escalation Stage

Patients will be administered DTP3 intravenously (i.v.), given as a one hr infusion three times per week (with an inter-dose interval of a minimum of 40 hr and a maximum of 72 hr) in continual 4-week cycles until disease progression or unacceptable toxicity, whichever occurs first.

In the dose escalation stage, the following maximum potential range of DTP3 dose levels will be examined:

2.0, 4.0, 6.0, 9.0, 12.0, 16.0, 20.0, 30.0, 45.0, 67.0, 98.0 mg/kg

The dose escalation will employ a flexible Bayesian Continuous Reassessment Methodology (CRM) to obtain the Maximum Tolerated Dose (MTD) of DTP3 associated with a target Dose Limiting Toxicity (DLT) of 30% from a range of up to 11 doses.

A TDSMC (Section 5.4) will review, on an ongoing basis, all available safety and efficacy/PD/PK data.

For the proposed design, the first patient will be given a starting dose of 2.0 mg/kg. If no DLT occurs, the next patient will only be dosed at the next higher dose after the preceding patient has completed 4 weeks of treatment.

The TDSMC may recommend increasing the number of patients at specific tolerable doses, to obtain further information to aid dose selection or evaluation of doses which are intermediate to the prespecified dose levels in order to further characterise the relationship between dose level and emergent toxicities.

If a DLT is observed at any dose level, dose escalation will revert to 3 patients per cohort (including the cohort with the initial DLT) to further assess the observed safety data. Once a DLT has been observed, the CRM model will commence estimating the DLT rate at each dose level and recommend the next best dose level with an estimated DLT rate closest to 30% for subsequent patients, using all the accrued DLT data at all doses. An empiric dose-toxicity model $F(\chi,\beta)=\chi^{A}exp(\beta)$, $0<\chi<1$ will be used, where the slope parameter β is assumed to follow a normal distribution with prior mean 0 and a pre-specified prior variance of 1.

The first patient in each cohort will not be enrolled until all patients at the immediately lower cohort have completed the DLT monitoring period and the TDSMC has reviewed the safety data to decide whether to proceed to the next dose level.

The CRM will continually re-estimate the MTD using all accrued DLT data during both the dose escalation and dose expansion stages.

At any time during the dose escalation stage, the TDSMC may recommend initiation of one or both expansion cohorts (MM and/or DLBCL) if it considers that a sufficiently strong efficacy signal and acceptable safety profile has been confirmed at that dose level (which will then be designated the RP2D level).

In this situation the TDSMC will decide whether the dose escalation stage should continue in parallel with the expansion stage, in order to further define the safety and tolerability of DTP3 up to a maximum tolerated dose, if this has not yet been determined.

If the TDSMC does not recommend a RP2D level prior to identification of the MTD, the committee will convene following determination of an MTD to review all available safety, efficacy, PK and PD data and formally recommend an RP2D level to take into the dose expansion stage. The **same** RP2D level will be evaluated in both the MM and DLBCL cohorts.

5.1.1 Dose Limiting Toxicities

Dose Limiting Toxicities (DLTs) are defined as the following events occurring within the first 28 days of dosing of DTP3, *i.e.* up to the end of Cycle 1, corresponding to 12 doses of DTP3 and which are considered to be at least **probably** related to DTP3:

- Any Grade 4 non-haematological adverse event not resolving to at least Grade 3 within 48 hrs
- Any Grade 3 non-haematological event not resolving to at least Grade 2 within 14 days

Excluding:

- Grade 3 nausea
- Grade 3 anorexia
- Grade 3 or 4 vomiting in patients who have not received optimal treatment with antiemetics
- Grade 3 or 4 diarrhoea in patients who have not received optimal treatment with antidiarrhoeal agents
- Grade 3 fatigue
- ≥Grade 3 laboratory abnormalities considered by the Investigator to be **not** clinically relevant
- ≥3 Grade 3 laboratory TLS if corrected by institutional management
- Grade 4 neutropenia for more than 7 days despite optimal growth factor support
- Grade 4 thrombocytopenia for more than 14 days (with or without platelet support) or associated with active bleeding at any time
- Any other toxicity judged by the TDMSC to be dose limiting in nature
- Death

To be **DLT evaluable**, a patient must have received at least 10 of the 12 scheduled doses of DTP3 (unless a DLT prevented further DTP3 dosing). Non-evaluable patients will be replaced for DLT estimation purposes but may remain in the study.

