5.5 Patient Withdrawal and Replacement

All patients should be treated until disease progression or unacceptable toxicity, whichever occurs first.

During the dose escalation stage, to be **DLT evaluable**, a patient must have received at least 10 of the 12 scheduled doses of DTP3 during Cycle 1 of treatment (in the absence of a DLT having interrupted DTP3 dosing). Non-evaluable patients will be replaced for DLT estimation purposes but may remain in the study.

During the dose expansion stage, patients who are withdrawn for reasons of disease progression and/or unacceptable toxicity will not be replaced. Patient who are not response evaluable may be replaced, after discussion with the medical monitor.

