5.7 Dose Modification

Dose Escalation Stage Only

- No dose reductions are permitted for any patient during the DLT evaluation period [Cycle 1 of DTP3).
- Patients experiencing a DLT may remain in the study at the originally assigned dose of DTP3 or a lower dose according to investigator judgement.

Patients initially entered into the study at a DTP3 dose level lower than the one currently being evaluated may increase their DTP3 dose level [provided they have not experienced a DLT during the DLT evaluation period] by one dose level increment per cycle, at the end of each cycle of treatment, at the discretion of the investigator, provided the DTP3 dose remains at least one level below the highest dose currently being evaluated **Dose Escalation and Expansion Stage**

- Up to **three** dose level reductions are permitted in the event of DTP3 related toxicity, at the discretion of the investigator.
- During the **dose escalation stage**, [for patients who have completed the initial DLT evaluation period] each dose reduction should be to the immediately preceding dose level specified in the DTP3 dose level escalation range [*e.g.* 20mg/kg reduced to 16mg/kg; 16mg/kg reduced to 12mg/kg *etc*]
- For the **dose expansion stage**, the TDSMC will specify a dose reduction algorithm at the time the RP2D level is determined, taking account of the actual RP2D level and the pattern of toxicities seen at lower dose levels during the dose escalation stage.
- Dose reductions are permitted for the following toxicities if they are considered clinically relevant by the investigator:
 - Any Grade 4 adverse event not resolving to at least Grade 3 within 48 hr
 - Any Grade 3 adverse event not resolving to at least Grade 2 within 14 days
 - Any dose delay greater than 7 days
- Any potential dose reduction must be discussed in advance with the Medical Monitor and (if judged appropriate by the investigator and medical monitor) the Chief Investigator too.
- If a dose level is reduced, it may be increased again (to the immediately preceding dose level), at the discretion of the investigator, if there is complete resolution of the original toxicity leading to the dose reduction.

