• Dose delays of up to 14 days are permitted for the resolution of DTP3 related toxicity. Patients requiring a dose delay greater than 14 days should be withdrawn from the study. Dose delays of greater than 14 days for reasons other than toxicity (*e.g.* logistical ones) must be discussed with and approved by the medical monitor.

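### Patients who lose three or more Cycle 1 doses to DTP3 toxicity that is not a listed DLT are replaced by default, so exclusion from the CRM depends on tolerability

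*Protocol*

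**What the plan says.** Section 5.1.1 sets the evaluability rule: "a patient must have received at least 10 of the 12 scheduled doses of DTP3 (unless a DLT prevented further DTP3 dosing". The synopsis and sections 3 and 5 repeat it. Section 5.5 words the exception as "in the absence of a DLT having interrupted DTP3 dosing" and adds: "Non-evaluable patients will be replaced for DLT estimation purposes but may remain in the study". A DLT is the only excuse for falling short.

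Section 5.7 governs what can happen to dosing in Cycle 1. In the escalation stage, "No dose reductions are permitted for any patient during the DLT evaluation period", while "Dose delays of up to 14 days are permitted for the resolution of DTP3 related toxicity".

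The DLT list in section 5.1.1 counts some toxicities only after a minimum duration, for example "Any Grade 3 non-haematological event not resolving to at least Grade 2 within 14 days" and "Grade 4 neutropenia for more than 7 days despite optimal growth factor support". Grade 4 thrombocytopenia without bleeding counts only beyond 14 days, and Grade 3 nausea, anorexia and fatigue are excluded. An open-ended item lets the TDSMC call another toxicity dose limiting; it is not tied to missed doses.

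Escalation runs with one patient per level until the first DLT. That DLT triggers cohorts of three and starts the CRM, which uses DLT data only (synopsis, section 5.1).

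**The concern.** The hold allowance, the DLT durations and the evaluability cut-off do not fit together. Toxicity can stop dosing long enough to fail the cut-off without lasting long enough to be a listed DLT. Followed as written, the rule replaces such a patient, so whether a patient contributes to the CRM depends on how well that patient tolerated the drug.

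This matters most in the one-patient stage. The only patient at a level can be unable to receive the schedule because of DTP3 and be replaced by one who can. The level then shows no DLT, and neither safeguard starts. Because replacement and escalation happen in real time, a later SAP cannot undo this.

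The expansion stage is handled differently. Section 5.5 does not replace patients withdrawn for unacceptable toxicity, and sections 5.2 and 5.4 keep patients with toxicity delays in the safety review. The escalation-stage rule has no counterpart.

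**Working it through.** **1. The cut-off.** DTP3 is "given as a one hr infusion three times per week" in 4-week cycles: 3 × 4 = 12 doses, as the protocol states. At least 10 are required, so a third missed dose makes the patient non-evaluable (12 − 3 = 9).

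**2. Doses lost to a hold.** Appendix C places doses on days 1, 3 and 5 of each week. If held doses are forfeited, and the hold starts after Dose 1 and lies wholly within Cycle 1:

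| Hold | Doses missed | Doses received |
|---|---|---|
| 5 or 6 days | 2 or 3 | 10 or 9 |
| 7 days | 3 | 9 |
| 10 days | 4 or 5 | 8 or 7 |
| 14 days | 6 | 6 |

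A hold that starts after Dose 10 can lose only Doses 11 and 12 within the 28 days. That leaves 10 of 12, and the patient stays evaluable. The protocol does not say whether delayed doses given after day 28 count; if they did, fewer patients would fail.

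**3. Against the DLT list.** Each toxicity below is not a listed DLT, yet a hold of the same length can fail the cut-off:

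- Grade 4 neutropenia for up to 7 days: 9 of 12 doses.
- Grade 4 thrombocytopenia without bleeding for up to 14 days: down to 6 of 12.
- A Grade 3 non-haematological event that resolves to Grade 2 within 14 days: down to 6 of 12.
- Grade 3 fatigue, nausea or anorexia: excluded whatever the duration.

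An event judged only possibly related cannot be a DLT either, because the definition requires at least a probable relationship.

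**4. Effect on the estimate.** Let p be the probability of a DLT and q the probability of non-DLT DTP3 toxicity that costs three or more doses. The protocol gives neither. Take p = 20% and q = 15% as an illustration:

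| Handling of the q group | Rate the CRM sees | Chance that a one-patient level passes |
|---|---|---|
| Replaced (as written) | p/(1−q) = 0.20/0.85 = 23.5% | (1−p−q)/(1−q) = 0.65/0.85 = 76.5% |
| Kept as non-DLT | p = 20% | 1−p = 80% |
| All called DLT | p+q = 35% | 1−p−q = 65% |

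Replacement therefore gives a figure above p and below p+q.

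**5. At the target.** If the rate among evaluable patients is r = 30%, then p = r(1−q) and the combined rate is r(1−q) + q:

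- q = 5%: 0.285 + 0.05 = 33.5%
- q = 10%: 0.27 + 0.10 = 37%
- q = 20%: 0.24 + 0.20 = 44%

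**6. Illustrative CRM.** The run used the protocol's empiric model, prior and 11 levels, with 24 patients and 1,500 simulated trials. The skeleton was assumed, as were DLT rates rising from 1% to 55% and q rising from 1% to 30%. The mean true combined rate at the selected MTD was 40% with replacement, 28% if all such patients were called DLTs, and 47% if they were kept as non-DLTs. Mean enrolment with replacement was 28.6 instead of 24. The protocol's own skeleton and scenarios are not in the document, so this run shows the ordering of the three options and not their size in this trial.

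**The case against.** The strongest objection concerns the benchmark. The design targets a 30% DLT rate, and replacement raises the estimate of that rate (20% to 23.5% in the example). A reader might infer that the CRM understates the DLT rate; the documents do not support that. The understatement appears only against p+q, which the protocol does not target. It follows that simply keeping these patients as non-DLTs would make matters worse: the estimate falls to 20% and the chance of passing rises to 80%. Both points stand.

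Second, the TDSMC reviews safety before each escalation, which in the one-patient stage means reviewing each patient. It can already call the event a DLT, and the patient is then evaluable; it can also add patients or use intermediate doses. This stands as mitigation, but it is discretionary. Nothing requires the question to be decided before replacement.

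Third, a reader might infer that the RP2D will be set at a dose many patients cannot receive. The documents do not show that. RP2D selection uses all safety, efficacy, PK and PD data. At least six patients must be treated at that level for 28 days or more before expansion (synopsis). Replaced patients remain in the safety set (section 8.2), and relative dose intensity is summarised by dose level (section 8.3).

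Fourth, holds are permitted and not required, treatment can also be stopped (section 4.3.1), and q may be small. The only clinical experience described, three patients at up to 2 mg/kg, had no event judged more than unlikely related. That limits what can be said about size, but it does not remove the gap at the higher levels.

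**Conclusion.** The point holds in a limited form. By default, the rule removes from the CRM patients who lose three or more doses to DTP3 toxicity that is not a listed DLT, and in a one-patient cohort this can let a level pass with neither safeguard triggered. The TDSMC can prevent it but is not obliged to.

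The quantity understated is the combined rate of DLT or toxicity-stopped dosing. At an observed 30%, it is 33.5% to 44% for q between 5% and 20%. These values of q are assumptions, and the upper comparison treats every such patient as informative about tolerability. The conclusion also assumes that held doses are forfeited, or at least do not count once given after day 28, and that the hold begins early enough to cost three doses.

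**What to change.** Reconcile the evaluability rule (synopsis, sections 3, 5, 5.1.1 and 5.5) with the DLT definitions and the delay allowance in section 5.7. This point takes no view on which hold length or DLT threshold is right.

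- Allow automatic replacement only when doses were missed for reasons unrelated to DTP3.
- For a patient below 10 of 12 doses because of DTP3-related toxicity, require the TDSMC to decide and record whether the event is a DLT under its existing open-ended item. The ruling must precede any replacement, escalation decision or CRM update.
- Enter those ruled DLT in the CRM. Do not enter the others as full non-DLT observations, since that would lower the estimate. Report them by dose level beside the DLT rate when the MTD and RP2D are chosen.
- State whether doses given after day 28 count towards the 10.

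The cost is protocol wording and one added TDSMC review item. Some levels may show more DLTs.
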